# 7.3. Lost to Follow-Up

A participant will be considered lost to follow-up if he or she repeatedly fails to return for scheduled visits and is unable to be contacted by the study site.

Site personnel are expected to make diligent attempts to contact participants who fail to return for a scheduled visit or were otherwise unable to be followed up by the site. Contact attempts should be documented in the participant's medical record.

If the participant continues to be unreachable, he or she will be considered to have withdrawn from the study.

# 8. Study Assessments and Procedures

Study procedures and the study visits at which they are performed, including tolerance limits for the study visits, are listed in the SoA (Section 1.3). Adherence to the study design requirements, including those specified in the SoA, is essential and required for study conduct.

# 8.1. Efficacy Assessments

#### Visits and order of efficacy assessments

Efficacy assessments occur as specified in the SoA (Section 1.3). Procedures at study visits should be timed so that participants' self-assessments, including Urticaria Patient Daily Diary (UPDD) and Dermatology Life Quality Index (DLQI), are completed before any clinical assessments or sample collections are performed.

Home or virtual health visits are permitted to evaluate clinical efficacy under special circumstances (for example, site closure or other restrictions), after consultation with the sponsor's medical monitor. The home or virtual health visits should be documented in the CRF. If required under special circumstances and after consultation with the sponsor's medical monitor, the DLQI can be read over the phone exactly as it is written, in the patient's native language, without any additional words or explanations. Responses should be documented by site staff, retained as source documentation, and entered into the CRF

#### Urticaria Patient Daily Diary (UPDD)

The UPDD is a daily diary completed twice per day (morning and evening) via an electronic, handheld device. Items asking about itch severity and number of hives pertain to the past 12 hours and are asked twice per day. The remaining items are asked once per day and pertain to the past 24 hours: interference with sleep, interference with daily activities, use of rescue medication (number of tablets), presence (and treatment) of angioedema, and any calls placed to healthcare professionals. While developed originally on paper, the electronic version of the UPDD has been shown to be equivalent to the paper version from a measurement perspective, and is considered a valid and reliable assessment of urticaria symptoms (Flood et al. 2013).

Pruritus, angioedema, and hives are monitored as clinical endpoints in the UPDD and would not constitute AEs. However, if any of these events is an SAE as defined in Appendix 10.3, Section 10.3.2, the event should be reported as an SAE. See Section 8.3.6 for more information.

There is no overall UPDD score calculation. The primary endpoint assessment (Urticaria Activity Score Over 7 Days [UAS7]) and key secondary endpoint assessments (Itch Severity Score Over 7 Days [ISS7] and Hives Severity Score Over 7 Days [HSS7]) are derived from data collected via the UPDD, as described below (Sections 8.1.1 and 8.1.2, respectively).

#### Appropriateness and devices/questionnaires for assessments

The UAS7, which is derived from the UPDD, has been used in previous CSU trials and is being used as the primary endpoint for trials conducted for registration (Xolair package insert, 2019; ligelizumab studies NCT03580369 and NCT03580356 [ClinicalTrials.gov]).

The secondary and exploratory measures of disease activity and quality of life in this study are also generally recognized as reliable, accurate, and relevant.

The self-reported questionnaires will be administered via either an electronic participant diary (UPDD) or on paper (DLQI), and in countries where the questionnaires have been translated into the native language of the region and linguistically validated.

#### 8.1.1. Primary Efficacy Assessment

#### 8.1.1.1. Urticaria Activity Score Over 7 Days (UAS7)

The weekly UAS7 is calculated using data from the UPDD. The UAS7 is the sum of the daily urticaria activity scores (UAS) over a 7-day period and ranges from 0 to 42. The daily UAS is the sum of the daily itch severity score (ISS) and daily number of hives score, and ranges from 0 to 6. The baseline UAS7 is the sum of the daily UAS over the 7 days prior to the first treatment. A higher UAS or higher UAS7 indicates greater urticaria disease activity.

The minimally important difference (MID) for UAS7 is defined as a reduction from baseline in weekly Urticaria Activity Score of 9.5 to 10.5 points or more (Mathias et al. 2015).

#### 8.1.2. Secondary Efficacy Assessments

#### 8.1.2.1. Itch Severity Score Over 7 Days (ISS7)

The weekly ISS7 is calculated using data from the UPDD. The ISS7 is the sum of the daily ISS over a 7-day period and ranges from 0 to 21. The daily ISS is the average of the morning and evening ISS on a 4-point scale of 0 (none), 1 (mild), 2 (moderate), and 3 (severe). The baseline ISS7 is the sum of the daily ISS over the 7 days prior to the first treatment. A higher ISS or higher ISS7 indicates more severe itching.

The MID for ISS7 is defined as a reduction from baseline in weekly itch severity score of 4.5 to 5.0 points or more (Mathias et al. 2015).

# 8.1.2.2. Hives Severity Score Over 7 Days (HSS7)

The weekly HSS7 is calculated using data from the UPDD. The HSS7 is the sum of the daily number of hives over a 7-day period and ranges from 0 to 21. The daily number of hives score (also called HSS) is the average of the morning and evening number of hive scores on a four-point scale of 0 (none), 1 (between 1 and 6 hives, inclusive), 2 (between 7 and 12 hives, inclusive), and 3 (greater than 12 hives). The baseline weekly HSS7 is the sum of the HSS over the 7 days prior to the first treatment. A higher HSS or higher HSS7 indicates a greater number of hives.

The MID for HSS7 is defined as a reduction from baseline in weekly number of hives score of 5.0 to 5.5 points or more (Mathias et al. 2015).

#### 8.1.3. Exploratory Assessments

#### 8.1.3.1. Dermatology Life Quality Index

The Dermatology Life Quality Index (DLQI) is a participant-rated, 10-item questionnaire that covers 6 domains including symptoms and feelings, daily activities, leisure, work and school, personal relationships, and treatment. The recall period of this scale is over the "last week." Response categories include "a little," "a lot," and "very much," with corresponding scores of 1,

2, and 3, respectively, and "not at all," or unanswered ("not relevant") responses scored as 0. Scores range from 0 to 30, with higher scores indicating greater impairment of quality of life. A DLQI total score of 0 to 1 is considered as having no effect on a participant's health-related quality of life (Hongbo et al. 2005), and a 4-point change from baseline is considered the minimal clinically important difference threshold (Basra et al. 2015).

# 8.2. Safety Assessments

#### Visits and order of safety assessments

Safety assessments occur at visits specified in the SoA (Section 1.3). Home or virtual health visits are permitted to assess the safety of the participant under special circumstances (for example, site closure or other restrictions), after consultation with the sponsor's medical monitor. The home or virtual health visits should be documented in the CRF.

If multiple safety assessments are scheduled for the same visit, the preferred order of completion is

- 1) ECG (if applicable) and vital signs first
- 2) other safety assessments, including physical examinations and AE collection, and finally
- 3) blood sample collection for clinical laboratory, PK, pharmacodynamic (PD), pharmacogenetic, biomarker, and immunogenicity testing.

#### Data collection and reporting

The AE data collection and reporting requirements are described in Section 8.3 and Appendix 10.3. Any clinically significant findings that result in a diagnosis and that occur after the participant receives the first dose of study drug should be reported to Lilly or its designee as an AE via eCRF. Additional requirements regarding adverse events of special interest are described in Section 8.3.

#### Safety monitoring

The principle investigator will monitor safety and laboratory data throughout the study and should discuss safety concerns with the sponsor immediately upon occurrence or awareness of the concern in order to determine whether the participant should continue or discontinue study drug.

The sponsor will periodically review evolving safety data, including AEs and SAEs, discontinuations, vital signs, concomitant medications, and medical history in monthly blinded reviews and via other appropriate methods. These methods include review by a functionally independent safety physician and/or clinical research scientist who regularly reviews SAE reports in real time and across studies, and reviews applicable clinical safety and epidemiological publications from the literature. If this safety monitoring uncovers an issue that needs to be addressed by unblinding at the individual or group level, additional analyses of the safety data can be performed by the sponsor's independent internal safety review committee.

#### Appropriateness of safety assessments

The safety assessments used in this study are routine elements of clinical health assessment and Phase 2 drug development.

As noted in Section 8.1, pruritus, angioedema, and hives are monitored as clinical endpoints and would not constitute AEs. However, if any of these events is an SAE as defined in Appendix 10.3, Section 10.3.2, the event should be reported as an SAE. See Section 8.3.6 for more information.

#### 8.2.1. Vital Signs

Measurements of vital signs (body temperature, blood pressure, and pulse rate) will be conducted at the study visits specified in the SoA (Section 1.3) and as clinically indicated. Additional vital signs may be measured during each study period as per judgment of the investigator.

Blood pressure and pulse rate should be measured after the participant has been sitting for at least 5 minutes. Orthostatic vital signs should be assessed, if possible, during any AE of dizziness or posture-induced symptoms. If orthostatic measurements are required, participants should be supine for at least 5 minutes and stand for at least 3 minutes. If the participant feels unable to stand, only supine vital signs will be recorded.

#### 8.2.2. Physical Examinations

One complete physical examination will be performed at Visit 1. This examination includes a visual examination of the skin and an assessment of peripheral lymph nodes but excludes pelvic, rectal, and breast examinations.

A symptom-directed physical examination that includes a visual examination of the skin will be performed at other visits, as specified in the SoA (Section 1.3) or as clinically indicated.

#### 8.2.3. Electrocardiograms

For each participant, 12-lead electrocardiograms (ECGs) will be collected as specified in the SoA (Section 1.3). Participants must be supine for approximately 5 to 10 minutes before ECG collection and remain supine but awake during ECG collection.

Electrocardiograms should be taken before collecting any blood for safety or PK tests; however, aberrations to this specified time will not be considered protocol deviations as long as the ECGs are taken and the actual recording time is documented. Electrocardiograms may be obtained at additional visits and times when deemed clinically necessary. Collection of additional ECGs is allowed to ensure high-quality records.

Electrocardiograms will be interpreted by a qualified physician (the investigator or qualified designee) at the study site as soon after the time of ECG collection as possible, and ideally while the participant is still present, to determine whether the participant meets the study entry criteria and for immediate participant management, should any clinically relevant findings be identified.

# 8.2.4. Chest Radiography

A posterior–anterior (PA) chest x-ray CXR, interpreted and reported by a radiologist or pulmonologist, will be obtained at screening, as specified in the SoA (Section 1.3). A lateral CXR can also be obtained if, in the opinion of the investigator, a lateral view is indicated.

Note: Participants do not need to have a CXR at screening if, based on the judgment of the investigator, both of the following two conditions are met:

- the CXR was performed within 6 months before initial screening, and
- documentation of the CXR, read by a qualified radiologist or pulmonologist, is sufficient for TB evaluation according to local standard of care.

For each participant, the CXR films or images or a radiology report must be available to the investigator for review before the participant is randomized. Certain findings from CXR may be consistent with a condition that excludes a participant from the study; see Section 5.2.

Note: Results of a chest computerized tomography (CT) scan or other imaging study similar to a CXR may be substituted in place of the CXR as described above, in consultation with the sponsor's medical monitor.

#### 8.2.5. Stool Testing

The stool evaluation will be conducted only for participants with certain risk factors and an eosinophil count >2 times ULN (Section 5.2). To be randomized, these participants must have a negative stool culture indicating no enteric pathogens (ova or parasites) are isolated.

Retesting is allowed within the screening period if there is a technical difficulty in performing or reporting the stool culture assay (Section 5.4.1).

#### 8.2.6. Laboratory Tests

Appendix 10.2 lists the clinical laboratory tests to be performed, and the SoA (Section 1.3) specifies the study visits at which samples are routinely collected for clinical laboratory tests.

Under special circumstances (for example, site closure or other restrictions), local laboratory testing is permitted after consultation with the sponsor's medical monitor as specified if indicated per PI to evaluate AEs .

If a participant elects, or is advised by the site, to have local labs drawn via home health or by presenting to a local lab, the lab analytes to be tested for safety assessment must be ordered at the local lab by the PI/site. The specific lab analytes for safety assessment will be determined in consultation with the sponsor's medical monitor. These analytes will be drawn, sampled, tested, and reported back to the PI/site. The PI must sign and date review of safety labs as per normal process.

Additional samples for laboratory testing will be obtained in the event of anaphylaxis or systemic allergic/hypersensitivity reactions, as described in Section 8.3.7.2 and Appendix 10.2. Additional tests may be performed at any time during the study as deemed necessary by the investigator or as required by local regulations.

All protocol-required laboratory assessments, as defined in Appendix 10.2, must be conducted in accordance with the laboratory manual and the SoA.

#### Reviewing and recording test results

The investigator must review the laboratory report, document this review, and record any clinically relevant changes occurring during the study in the AE section of the CRF. The laboratory reports must be filed with the source documents.

If laboratory values from non-protocol-specified laboratory assessments performed at the institution's local laboratory require a change in participant management or are considered clinically significant by the investigator (for example, SAE or AE or dose modification), the results must be recorded in the CRF.

#### Repeat testing after clinically significant abnormal findings

Clinically significant abnormal laboratory findings are those that are not associated with the underlying disease, unless judged by the investigator to be more severe than expected for the participant's condition. Laboratory tests with values that are clinically significantly abnormal during participation in the study or within 12 weeks after the last dose of study intervention should be repeated until the values return to normal or baseline or are no longer considered clinically significant by the investigator or medical monitor. If the values do not return to normal/baseline within a period of time judged reasonable by the investigator, the etiology should be identified and the sponsor notified.

#### Blinding of laboratory test results

Laboratory results that could unblind the study will not be reported to investigative sites or other blinded personnel (Appendix 10.2).

#### Sample retention

Unless otherwise specified in the subsections of Section 8 or in Appendix 10.1, Section 10.1.12 ("Long-Term Sample Retention"), all samples collected for specified laboratory tests will be destroyed within 60 days of receipt of confirmed test results. Certain samples may be retained for a longer period, if necessary, to comply with applicable laws, regulations, or laboratory certification standards.

#### 8.2.6.1. Pregnancy Testing

Pregnancy testing is to be performed on women of childbearing potential and women with a history of tubal ligation (see Section 5.1). Participants who are pregnant will be discontinued from the study (Section 7.1.1).

#### Visits and times

Serum pregnancy test will be done at screening only, and results will be confirmed by the central laboratory.

Urine pregnancy testing will be performed locally at visits specified in the SoA (Section 1.3). The urine pregnancy test must be "negative" within 24 hours prior to administration of study drug at every study visit.

Urine pregnancy testing may be performed at additional time points during the treatment period and/or follow-up period, at the discretion of the investigator or if this is required by local regulations.

If a urine pregnancy test is not available, a serum pregnancy test is an acceptable alternative.

#### Optional FSH Testing

Assessment of FSH levels can assist in determining if a woman meets the definition of "postmenopausal" as described in Section 5.1. The participant's FSH level can be obtained

during screening at the discretion of the investigator. The FSH level can also be optionally obtained during the study to determine the participant's postmenopausal status (see Section 1.3 and Appendix 10.2).

#### 8.2.7. Tuberculosis Testing and Monitoring

#### Tuberculosis Testing

During screening, all participants are to be assessed for risk factors, symptoms, and signs of TB with all of the following:

- Thorough history to determine the lifetime risk factors for TB infection, for TB progression, and for symptoms and/or signs of active TB, and
- Signs of previous or active TB by means of
  - Thorough physical examination for signs of active TB, including measurement of body temperature and assessment of peripheral lymph nodes (Section 8.2.2), and
  - PA CXR interpreted and reported by radiologist or pulmonologist (Section 8.2.4).

All participants with no history of LTBI or active TB, and no history of positive Mantoux tuberculin skin test (TST) using purified protein derivative (PPD) or positive *Mycobacterium tuberculosis* interferon gamma release assay (IGRA) must have one of the following:

- Purified Protein Derivative (PPD) TST
  - The TST is performed by injecting 0.1 mL of tuberculin PPD into the inner surface of the forearm. The injection should be made with a tuberculin syringe, with the needle bevel facing upward. The TST is an intradermal injection. When placed correctly, the injection should produce a pale elevation of the skin (a wheal) 6 to 10 mm in diameter. Measure induration at site of intradermal injection 48 to 72 hours after intradermal injection. Test must be read during this window of time. The reaction should be measured in millimeters of induration (palpable, raised, hardened area or swelling). The reader should not measure erythema (redness). The diameter of the indurated area should be measured across the forearm (perpendicular to the long axis).
  - An induration of 5 or more millimeters is considered positive in
    - ¤ HIV-infected persons
    - ¤ A recent contact of a person with TB disease
    - III Persons with fibrotic changes on chest radiograph consistent with prior TB
    - ¤ Persons with organ transplants
    - $\approx$  Persons who are immunosuppressed for other reasons (for example, taking the equivalent of >15 mg/day of prednisone for 1 month or longer, taking tumor necrosis factor- $\alpha$  antagonists)
  - An inducation of 10 or more millimeters is considered positive in all other potential clinical trial participants.

- Two-step testing (repeat TST 1 to 3 weeks after the first TST) is recommended for certain participant groups, including:
  - ¤ persons receiving immunosuppressant treatment
  - ¤ persons with a history of temporally remote increased risk of TB infection
  - persons for whom the first test is negative, as per local public health and/or professional medical society recommendations.
- Interferon Gamma Release Assay (IGRA) for *M tuberculosis*. Ensure that specimen handling, transport, timing, and laboratory procedures meet all requirements per package insert. If the investigator suspects a false-positive IGRA result in a participant with no increased risk of TB infection during lifetime, and no evidence of prior or current TB on physical examination and/or on CXR interpreted by radiologist and/or pulmonologist (investigator assessment by history and physical examination, and CXR report documented in eCRF), the investigator may discuss retesting with the sponsor's designated medical monitor.

#### Retesting

One retest is allowed for participants with an "indeterminate" QuantiFERON-TB Gold assay or "borderline" T-SPOT assay. Participants with 2 indeterminate QuantiFERON-TB Gold assays or 2 borderline T-SPOT assays will be excluded.

#### Diagnosed LTBI

Participants diagnosed with LTBI are excluded unless they are candidates for LTBI treatment, are treated for LTBI, and the following criteria are met:

- After receiving at least 4 weeks of appropriate LTBI therapy (as per World Health Organization and/or the United States Centers for Disease Control guidelines), there is no evidence of hepatotoxicity (ALT/AST must remain ≤2 times ULN) or other treatment intolerance. The participant may be rescreened, and is not excluded due to LTBI.
- The participant must continue and complete appropriate LTBI therapy in order to remain eligible to continue to receive study intervention.

#### 8.2.8. Hepatitis B Testing and Monitoring

Initial testing for HBV infection includes hepatitis B surface antigen (HBsAg) and antibody to hepatitis B core antigen (anti-HBc).

- If HBsAg is positive, the participant is excluded.
- If HBsAg is negative and anti-HBc is negative, the participant is not excluded.
- If HBsAg is negative and anti-HBc is positive, the participant is excluded.

#### 8.2.9. Hepatitis C Testing and Monitoring

Initial testing for HCV infection includes testing for antibodies to HCV.

• If anti-HCV is positive, a serum test for circulating HCV RNA is required.

- If HCV RNA test is negative, the participant is not excluded.
- If HCV RNA test is positive, the participant is excluded (see Section 5.2).

Participants who have had HCV infection and been successfully treated, defined as a sustained virologic response (HCV RNA by polymerase chain reaction (PCR) negative for at least 24 weeks following treatment completion) are not excluded on the basis of HCV as long as HCV RNA test is negative at screening.

If HCV RNA is detected during the study, the study drug will be discontinued (Section 7.1.1), and the participant should receive appropriate follow-up medical care.

#### 8.2.10. Hepatic Safety Monitoring

If a study participant experiences elevated ALT  $\geq$ 3 times ULN, ALP  $\geq$ 2 times ULN, or TBL  $\geq$ 2 times ULN, liver testing (described in Appendix 10.5) should be repeated within 3 to 5 days including ALT, AST, ALP, TBL, direct bilirubin, gamma-glutamyl transferase, and creatine kinase to confirm the abnormality and to determine if it is increasing or decreasing. If the abnormality persists or worsens, clinical and laboratory monitoring and evaluation for possible causes of abnormal liver tests should be initiated by the investigator in consultation with the study medical monitor. Monitoring of ALT, AST, TBL, and ALP should continue until levels normalize or return to approximate baseline levels.

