#### Hepatic Event or Liver Test Abnormality

• Participants who are discontinued from study drug because of a hepatic event or liver test abnormality should have additional hepatic safety data collected via the hepatic eCRF packet.

Discontinuation of study drug because of abnormal liver tests should be considered by the investigator when a participant meets one of the following conditions after consultation with the medical monitor (see Section 8.2.10):

- ALT or AST >8 times ULN
- ALT or AST >5 times ULN sustained for more than 2 weeks
- ALT or AST >3 times ULN and TBL >2 times ULN or international normalized ratio (INR) >1.5
- ALT or AST >3 times ULN with the appearance of fatigue, nausea, vomiting, right upper-quadrant pain or tenderness, fever, rash, and/or eosinophilia (>5%)
- ALP >3 times ULN
- ALP >2.5 times ULN and TBL >2 times ULN, or
- ALP >2.5 times ULN with the appearance of fatigue, nausea, vomiting, right upper quadrant pain or tenderness, fever, rash, and/or eosinophilia (>5%).

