#### Hepatic Safety Data Collection

Additional safety data should be collected via the hepatic eCRF packet if 1 or more of the following conditions occur:

- elevation of serum ALT to  $\geq$ 5 times ULN on 2 or more consecutive blood tests
- elevated serum TBL to  $\geq 2$  times ULN (except for cases of known Gilbert's syndrome)
- elevation of serum ALP to  $\geq 2$  times ULN on 2 or more consecutive blood tests
- participant discontinued from treatment due to a hepatic event or abnormality of liver tests, or
- hepatic event considered to be an SAE.

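### An isolated AST rise can meet a criterion for considering discontinuation, yet it triggers neither the 3-to-5-day liver retest nor the laboratory route to the hepatic eCRF packet.

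*Protocol*

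**What the plan says.** Protocol 8.2.10 (Hepatic Safety Monitoring) sets the retest rule. It begins "If a study participant experiences elevated ALT" at or above 3 times ULN, or ALP or total bilirubin at or above 2 times ULN; in those cases "liver testing (described in Appendix 10.5) should be repeated within 3 to 5 days". The stated purpose is "to confirm the abnormality and to determine if it is increasing or decreasing". AST, GGT and creatine kinase are in the panel to be repeated, and AST is among the tests then followed until they settle. AST is not among the values that start the process.

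Under Hepatic Safety Data Collection, the laboratory triggers for the hepatic eCRF packet are "elevation of serum ALT to" at least 5 times ULN on two or more consecutive tests, total bilirubin at least 2 times ULN (known Gilbert's syndrome excepted), and ALP at least 2 times ULN on two or more consecutive tests. The other triggers are a hepatic SAE and "participant discontinued from treatment due to a hepatic event or abnormality of liver tests".

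Protocol 7.1.1 (Hepatic Event or Liver Test Abnormality) lists when the investigator should consider stopping study drug, in consultation with the medical monitor, and cross-refers to 8.2.10. The first entry is "ALT or AST >8 times ULN". The other three aminotransferase entries name both enzymes in the same way.

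**The concern.** Section 7.1.1 treats a raised AST as sufficient reason to consider stopping drug. The section it refers to for follow-up does not treat the same AST value as a reason to retest. When confirmation happens then depends on the investigator's judgment, whereas an equal ALT rise has a 3-to-5-day step. The work-up for causes in 8.2.10 follows from the abnormality persisting or worsening on retest, so it has no AST starting point either. The 7.1.1 criterion of more than 5 times ULN sustained for over 2 weeks needs repeat values, and no AST result sets a date for one.

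If drug is continued and there is no hepatic SAE, the hepatic packet may not be collected. The same applies to a rise after the last dose, when there is no drug left to stop. What is at stake is patient safety and the completeness of the safety data. The primary analysis and power are not involved.

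**Working it through.** The plan states no figure on this point to reproduce. The check is a comparison of triggers, followed by the spacing of scheduled chemistry.

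**Triggers side by side**

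| Rule | ALT | AST | ALP | Total bilirubin |
|---|---|---|---|---|
| 8.2.10 retest in 3 to 5 days | ≥3× ULN | none | ≥2× | ≥2× |
| Packet, laboratory triggers | ≥5×, 2 or more tests | none | ≥2×, 2 or more tests | ≥2× |
| 7.1.1, consider stopping | >8×; >5× for over 2 weeks; >3× with bilirubin >2× or INR >1.5; >3× with symptoms or eosinophilia | same as ALT | >3×; >2.5× with bilirubin >2× or with symptoms or eosinophilia | only in combination |
| SAP 5.7.6.1 listing | ≥3×, ≥5×, ≥10× | ≥3×, ≥5×, ≥10× | ≥1.5× | ≥2× |

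**Test case.** Take AST above 8 times ULN with ALT below 3×, ALP below 2× and bilirubin below 2×. It meets 7.1.1 on one value, does not start the retest, and meets no laboratory trigger for the packet. Where AST above 3× comes with bilirubin above 2×, bilirubin itself starts the retest and, Gilbert's syndrome apart, the packet. The gap is therefore confined to AST rises without another trigger.

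**Time to the next scheduled AST.** Chemistry includes AST (Appendix 10.2) and is drawn at every visit in Tables 1 and 2.

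- Study days V2 to V16: 1, 8, 15, 29, 43, 57, 71, 85, 92, 99, 113, 127, 141, 155, 169. Follow-up: 197 (V801) and 239 (V802).
- Visit tolerances: none at V2, ±1 at V3, ±3 at V4 to V16, ±7 at V801 and V802.
- Range of an interval = difference in nominal days ± the sum of the two tolerances. Nominal excess = nominal interval − 5 days.

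| Interval | Nominal days | Range | Excess over 5 |
|---|---|---|---|
| V2–V3 | 7 | 7 ± 1 = 6 to 8 | 2 |
| V3–V4 | 7 | 7 ± 4 = 3 to 11 | 2 |
| V9–V10, V10–V11 | 7 | 7 ± 6 = 1 to 13 | 2 |
| Other 10 treatment intervals | 14 | 14 ± 6 = 8 to 20 | 9 |
| V16–V801 | 197 − 169 = 28 | 28 ± 10 = 18 to 38 | 23 |
| V801–V802 | 239 − 197 = 42 | 42 ± 14 = 28 to 56 | 37 |

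The first four rows make 14 treatment intervals: 4 of 7 days and 10 of 14 days. Nine of the ten 14-day intervals end on a dosing visit (V5 to V9 and V12 to V15). In those, absent earlier action, the next AST sample is drawn on the day of the next infusion, whereas a 3-to-5-day retest would come before it.

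If drug is permanently stopped, the early termination visit adds a chemistry draw. V801 then follows at 28 ± 7 = 21 to 35 days, taking the termination visit date as fixed because the schedule gives it no window.

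**The case against.** The two sections do different jobs: 7.1.1 says when to consider stopping, and 8.2.10 says when to retest and complete extra forms. Nothing requires identical triggers, and AST can rise for non-hepatic reasons, which could justify an ALT-only trigger. The retest is worded as a recommendation. Several other provisions also apply:

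- Under Safety monitoring in 8.2, the investigator "should discuss safety concerns with the sponsor immediately upon occurrence or awareness of the concern".
- Section 8.2.6 requires review of every laboratory report, allows additional tests at any time, and asks for clinically significant values to be repeated up to 12 weeks after the last dose. For completers that is Day 155 + 84 = Day 239, the nominal day of V802.
- Section 8.3.3 requires follow-up of medically important or related AEs, and Appendix 10.5 allows extra hepatic sampling.
- Stopping drug for the rise, or a hepatic SAE, brings in the packet.
- The SAP lists raised AST values for Periods 2 and 3, so the values are not lost.

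Much of this stands and limits the weight of the point. The 23- and 37-day excesses fall after dosing has ended, so they bear on follow-up and data capture and not on 7.1.1. Three of the four 7-day intervals can also fall within 5 days inside the visit windows.

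The difference between the enzymes remains. None of these provisions dates a repeat for AST. They cover ALT equally, and the sponsor still gave ALT a timed step. The documents offer no reason for the distinction. They treat the enzymes alike in exclusion criterion 27a, the latent tuberculosis rules, 7.1.1 and SAP 5.7.6.1. Non-hepatic origin is a question the retest panel helps to answer, since it already contains creatine kinase.

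**Conclusion.** The concern holds as a minor inconsistency in safety monitoring. An isolated AST rise can meet a 7.1.1 criterion with no timed confirmation, and the hepatic packet may be missed if drug is continued or the rise comes after the last dose. During treatment, the nominal delay beyond the 5-day limit is 2 days in 4 intervals and 9 days in 10. Those figures assume that nobody repeats the test before the next scheduled visit. They are the delay the schedule permits; they do not predict what a site would do with a very high value.

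Discontinuation is not blocked, because it can be considered on the first result. The number of participants affected cannot be derived from the documents and may be zero. No efficacy result changes.

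**What to change.** Make two wording changes in Protocol 8.2.10:

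- In the retest rule, replace the ALT condition with *ALT or AST ≥3 times ULN*.
- In the packet list, replace the ALT condition with *serum ALT or AST ≥5 times ULN on 2 or more consecutive blood tests*.

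The cost is a few additional blood draws and hepatic eCRF packets, some of them for AST rises that prove not to be hepatic. If the ALT-only trigger was intended, one sentence giving the reason would settle the discrepancy with 7.1.1, although AST would still have no timed retest.
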